12.1. RATIONALE FOR THE SELECTION OF THE DOMAIN FOR THE TRIAL'S PRIMARY OUTCOME

This study aims to evaluate the safety and tolerability of exposure to stroboscopic light in individuals with MDD and to collect critical data on the stroboscopic parameters that reliably elicit tolerable, comfortable, and engaging experiences.

Tolerability is assessed by participants selecting which side effects they experienced, if any. The potential side effects are drawn from three of the Visual Discomfort Questionnaire's (VDQ) subscales: sickness, eye discomfort and head discomfort (Vinkers et al., 2024). The VDQ was developed to measure the discomfort caused by various visual stimuli. In this study, the subscale for side effects on vision is omitted, as participants will have their eyes closed during the strobe sessions, and visual hallucinations are considered part of the experience. A 10-point scale is used to signify the severity of symptom discomfort, allowing for an immediate understanding of participants' tolerance levels; this measure comprises their tolerability score.

12.2. IF THE ANALYSIS METRIC FOR THE PRIMARY OUTCOME REPRESENTS WITHIN-PARTICIPANT CHANGE, DEFINE AND JUSTIFY THE MINIMAL IMPORTANT CHANGE IN INDIVIDUALS

This does not apply to the current study.

12.3. IF THE OUTCOME DATA COLLECTED ARE CONTINUOUS BUT WILL BE ANALYZED AS CATEGORICAL, SPECIFY THE CUTOFF VALUES TO BE USED

This is not applicable to this research study.

12.4. IF OUTCOME ASSESSMENTS WILL BE PERFORMED AT SEVERAL TIME POINTS AFTER RANDOMIZATION, STATE THE TIME POINTS THAT WILL BE USED FOR ANALYSIS

No randomisation or blinding will take place in this study.

After each 2-minute strobe session participants will answer questions regarding potential side effects, tolerability and their overall stroboscopic experience.

12.5. IF A COMPOSITE OUTCOME IS USED, DEFINE ALL INDIVIDUAL COMPONENTS OF THE COMPOSITE OUTCOME

In addition to the session-specific tolerability rating, we will ask participants to indicate (if possible) in which 30-second section of a session these side effects occurred. The session-specific tolerability score is defined as the highest tolerability score reported for any present side effects during that block.

13.

TIME SCHEDULE OF ENROLLMENT, INTERVENTIONS, ASSESSMENTS, AND VISITS FOR PARTICIPANTS (A SCHEMATIC DIAGRAM IS HIGHLY RECOMMENDED)

Pre-trial: Through an online Qualtrics survey: information sheet provided to the participant, consent form, pre-screening and demographic questions, PHQ-9 and M3VAS.

Weeks 1-6: Experimentation, 60 minutes per participant.

Weeks 6+: Data analysis and research and development to create the intervention that will be used in WP2.

14. ESTIMATED NUMBER OF PARTICIPANTS NEEDED TO ACHIEVE STUDY OBJECTIVES AND HOW IT WAS DETERMINED

Based on guidelines for the required sample size for a pilot/feasibility trial to precisely estimate the standard deviation (SD) of a normally distributed variable (session tolerability score) we will use a sample size of 25 (Whitehead et al., 2016). Anticipating a maximum dropout rate of 20% the total sample size required for this study is 32 (WP1).

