8. TRIAL DESIGN

This is a single-arm safety and tolerability study (with dose escalation).

METHODS: PARTICIPANTS, INTERVENTIONS, AND OUTCOMES

9. DESCRIPTION OF STUDY SETTING AND LIST OF COUNTRIES WHERE DATA WILL BE COLLECTED

Demographic information and inclusion criteria data will be collected online via Qualtrics; participants will be excluded at this point if they are not eligible based on the outlined inclusion and exclusion criteria.

Testing will take place within the Sussex Centre for Consciousness Science's laboratory, on the University of Sussex Falmer Campus. Participants are tested within a sound-proof booth with computer equipment to record their answers using the online-survey tool Qualtrics between strobe sessions, with the strobe light being placed on the outside of the window of the booth.

All testing will take place in Brighton, England.

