After each 2-minute session, participants will be asked whether they had any side effects; if they select no, they will not be asked any further information regarding the tolerability of the current session. If participants indicate that they experienced adverse effects, they will be presented with a list of symptoms from the Visual Discomfort Questionnaire to select the frequency at which each symptom occurred (Vinkers et al., 2024). Any reported side effect will then be rated on a 10-point scale, this will be referred to as the *tolerability score* or symptom discomfort score, the scale ranges from 0 (no symptom discomfort) to 10 (worst possible symptom discomfort), with 3 indicating mild symptom discomfort, 5 moderate symptom discomfort, and >7 severe symptom discomfort. Any report of a scorer >7 will result in that parameter's testing being stopped immediately to avoid further discomfort.

Participants will also report their overall experience on a 0-100 sliding scale via Qualtrics, asking the participant to report how engaging, pleasurable, overall uncomfortable, and sleepy each session was.

After each round of questions, participants will have an opportunity to share their thoughts on the session and also have a break.

To ensure that the experimental procedure has not inadvertently increased participants' depressive symptoms, participants will fill out the M3VAS change and the PHQ-9 again at the end of the testing session. If participants report a deterioration in well-being as indexed by any increase in M3VAS scores in the pre-to-post measurements, support will be offered and the participant referred to relevant sources of support, such as the University of Sussex-specific counselling services for students, as well as their GP, general non-emergency mental health support, or local A&E services, depending on the severity of symptoms.

After the administration of all sessions and questionnaires, participants will be debriefed; this will be the end of the testing session.

B. CRITERIA FOR DISCONTINUING OR MODIFYING ALLOCATED INTERVENTIONS FOR A GIVEN TRIAL PARTICIPANT

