To test whether 30-second sections within the strobe sessions are tolerable, participants' maximum tolerability score within each section is considered. If participants don't report any negative symptoms, their tolerability score across the relevant sections will be recorded as 0.

A parameter's 30-second section will be considered tolerable if, across participants, the upper limit of the 80% confidence interval for reported tolerability scores is less than 7.

Secondary outcomes will be evaluated through exploratory analyses, such as examining the frequency of any side effects, engagement, arousal, overall discomfort and enjoyment. These analyses will be descriptive, utilizing data visualizations and descriptive statistics to explore patterns across sessions, both within and between participants.

A1. DESCRIBE ANY PLANNED METHODS TO ACCOUNT FOR MULTIPLICITY IN THE ANALYSIS OR INTERPRETATION OF THE PRIMARY AND SECONDARY OUTCOMES

This is not applicable to this research study.

B. METHODS FOR ANY ADDITIONAL ANALYSES

Secondary outcomes will be explored through data descriptors (i.e. means, standard deviations) and graphs comparing them between sessions within and between participants. Due to expected low power of any such comparisons no inferential statistical analysis will be performed. These explorations will be used to identify potential trends and patterns, but will not be used to infer any relationships between variables.

C. DEFINITION OF ANALYSIS POPULATION RELATING TO PROTOCOL NON-ADHERENCE, AND ANY STATISTICAL METHODS TO HANDLE MISSING DATA

Data from participants who do not attend the experimental testing or withdraw before the administration of any strobe sessions will not be included in the analyses of the intervention's tolerability.

However, if a participant discontinues their participation due to discomfort during the strobe sessions, their partial data up to the point of withdrawal will be included in the analysis.

Data from all participants completing the sign-up form, regardless of their eligibility will be recorded and stored to quantify interest in these strobe light experiments.

The data of any participant requesting their data to be withdrawn from the study, within 2 weeks of the end of testing will be deleted and excluded from all analysis.

METHODS: MONITORING

21.

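### Visual disturbance that outlasts the light has no dedicated item in the symptom list, because the reasons for dropping the vision subscale apply only while the light is on

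*Protocol*

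**What the plan says.** Section 12.1 of the protocol defines the content of the tolerability measure: "The potential side effects are drawn from three of the Visual Discomfort Questionnaire's (VDQ) subscales: sickness, eye discomfort and head discomfort". The fourth domain is left out on purpose: "the subscale for side effects on vision is omitted, as participants will have their eyes closed during the strobe sessions". A second reason follows: "visual hallucinations are considered part of the experience".

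The timing is in section 12.4: "After each 2-minute strobe session participants will answer questions regarding potential side effects, tolerability and their overall stroboscopic experience". Section 9 (study setting) says that participants have "computer equipment to record their answers using the online-survey tool Qualtrics between strobe sessions".

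The subsection on interventions describes the route into the score. A yes/no question on side effects comes first. Participants who answer yes go on to the list: "they will be presented with a list of symptoms from the Visual Discomfort Questionnaire to select the frequency at which each symptom occurred". Reported symptoms are then rated 0 to 10 (same subsection; appendix 33e). The highest rating forms the score (sections 12 and 12.5). For participants without symptoms, section 20A adds: "If participants don't report any negative symptoms, their tolerability score across the relevant sections will be recorded as 0". A section of 30 seconds counts as tolerable if the upper 80% confidence limit across participants is below 7 (section 20A), and that result selects the parameters for WP2 (section 12).

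**The concern.** The justification and the measurement refer to different times. Closed eyes and intended imagery explain why visual effects should not count as harms while the strobe runs. They do not explain why vision should go unasked once the strobe has stopped and the participant is reading a screen. Blur or a persistent afterimage at that point is an after-effect of the exposure and not part of the intended experience.

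This is a first tolerability study of this stimulus in people with depression, and the stimulus is light directed at closed eyes. The same symptom list feeds three things: the primary tolerability score, the provisions that halt testing on a high score, and the secondary outcome describing the kind, frequency and strength of symptoms. WP2 sessions last 30 minutes against 2 minutes here, so the symptom profile from WP1 is what the next stage has to build on. A domain that was not asked about cannot be recovered after data collection.

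**Working it through.** The point concerns the content of an instrument, so the main check is to trace the measurement path. One calculation then shows how far the gap could reach into the pass/fail decision.

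**Path of a lingering visual effect**

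1. *Reasons for omission (section 12.1).* Eyes closed during the strobe; hallucinations are part of the experience. Both refer to the stimulation period.
2. *Time of rating (sections 9 and 12.4, interventions subsection).* After each 2-minute session, on a computer. Open eyes are not stated but follow from answering an on-screen survey.
3. *First question.* A participant whose only complaint is disturbed vision can answer yes.
4. *List.* Sickness, eye discomfort and head discomfort. The protocol treats vision as a separate subscale and removes it, so there is no dedicated item. This holds for all 11 sessions.
5. *Rating.* Appendix 33e has participants rate the symptoms they reported. If reporting means selecting from the list, the visual effect gets no rating. The interventions subsection and section 22, however, speak of rating reported side effects or symptom discomfort in general, without limiting this to the list. The text does not settle which applies.
6. *Other routes.* The 0-100 slider for overall discomfort, the open comment after each session, and solicited and spontaneous adverse event reporting (section 22). The slider and the comment are not specific to vision and do not enter the 0-10 score, and section 22 describes no visual item.

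**Reach into the pass/fail decision**

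Inputs: n = 25 (section 14); threshold 7 and 80% limit (section 20A). Assumptions: the interval is a two-sided t interval for the mean, which the protocol does not specify; k participants rate the visual effect at the maximum of 10; everyone else scores 0.

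- Mean = 10k/25
- SD = 10 × √[(k/25)(1 − k/25) × 25/24]
- Upper limit = mean + t × SD/√25, with t = 1.318 (90th percentile, 24 degrees of freedom)

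| k | Mean | SD | Upper 80% limit | Result |
|---|---|---|---|---|
| 14 | 5.60 | 5.07 | 5.60 + 1.318 × 1.013 = 6.94 | passes |
| 15 | 6.00 | 5.00 | 6.00 + 1.318 × 1.000 = 7.32 | fails |

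Even with the item in place, 14 of 25 participants (56%) at the worst possible rating would not fail a section on this effect alone. Non-zero scores from other symptoms would lower the number needed; ratings below 10 would raise it. The documents give no frequency or severity for visual after-effects.

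**The case against.** The strongest case against is that the omission is disclosed and reasoned, and that other routes remain open. Section 22 prompts for discomfort and side effects in broad terms, a researcher is present throughout, participants can stop on request, and medical incidents are a separate primary outcome. Section 12 says that overall discomfort will also inform WP2, so the tolerability score is not the only discomfort measure that reaches that decision. The VDQ items are not reproduced, so a retained eye-discomfort item may partly cover after-effects, and the omitted subscale may not ask about them at all.

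Much of this stands, and it rules out several stronger readings that a reader might infer:

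- *Lingering visual effects go entirely unrecorded.* Not supported, given the slider, the comments, adverse event reporting and the broad wording on what is rated.
- *Such a participant is scored 0.* Not established. Section 20A assigns 0 to those who report no negative symptom, and someone who answered yes has reported something. The protocol does not say what score follows.
- *The omission would cause an intolerable setting to be passed into WP2.* The calculation shows that the section decision would nearly always be the same with the item included.
- *The whole vision subscale must be restored.* This would rest on item wording that the document does not show.

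What the objection does not remove is the mismatch itself. Neither stated reason covers the period after the light, and none of the remaining routes is described as asking about vision.

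**Conclusion.** The point holds as a limited gap in solicited harms. Visual disturbance that persists after the light stops has no dedicated item in the list behind the tolerability score, the score-based halting provisions and the secondary symptom profile, and the protocol does not make clear whether an unlisted symptom would be scored.

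The loss falls mainly on the individual participant's score and on the description of symptoms. The across-participant decision would change only if such effects were common and severe: at least 15 of 25 at the maximum rating, if nothing else is reported and the interval is a two-sided t interval for the mean. The conclusion rests on two inferences: that eyes are open while the survey is answered, and that the retained eye-discomfort items do not already ask about vision after exposure. The second cannot be checked from the protocol. The change is worth making because it is cheap, not because the trial's conclusions depend on it.

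**What to change.** In section 12.1, add to the symptom list at least one item on visual disturbance still present after the light has stopped and the eyes are open, or use those VDQ vision items that fit this description. The wording should exclude imagery seen during the strobe, which preserves the reason for the omission. Rate the item on the same 0-10 scale and include it in the maximum that forms the tolerability score. In the same place, state that any symptom not on the list is rated and counted in the same way, and align the interventions subsection, section 22 and appendix 33e with that statement.

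The cost is one or a few questionnaire items, shown only after a yes to side effects. No threshold or halting provision changes. The small downside is that some harmless, brief afterimages will be reported; these should receive low discomfort ratings.

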Within the current study, a maximum luminance of 3800 lux over the participant's (closed) eyes at a distance of 1 meter will be used. Previous research has administered stroboscopic light successfully to influence mood states; our research expands this literature by assessing the safety and tolerability of this approach in the MDD population (Johnson et al., 2024).

Participants will undergo 11 stroboscopic sessions of increasing subjective 'intensity', following a fixed order, each lasting 2 minutes. The first 10 sessions are divided into four 30-second sections to test incremental changes in parameters; luminance, stimulation frequency, rapid frequency changes, and duty cycles. Initial sections are designed to induce minimal effects, with subsequent sections using a staircase method to gradually increase the intensity of the stroboscopic experience (see Figure 2). The final session (session 11) will contain a combination of all tested parameters.

| | 1 | 1 | |
|----------------|---------------------------|------------|---|
| Session Number | Tested Parameters | Split | Steps |
| 1 | Luminance | 4 x 30 sec | 10, 30, 50, 70 |
| 2 | Luminance | 4 x 30 sec | 70, 80, 90, 100 |
| 3 | Frequency | 4 x 30 sec | 3, 5, 7, 9 |
| 4 | Frequency | 4 x 30 sec | 9, 11, 13, 15 |
| 5 | Frequency Shift Small | 4 x 30 sec | 3, 3.75, 4.69, 5.82 (multiplicative ratio of 1.25x base Hz, a major third) |
| 6 | Frequency Shift Moderate | 4 x 30 sec | 3, 4.5, 6.75,10.13 (multiplicative ratio of 1.5x base Hz, a perfect fifth) |
| 7 | Frequency Shift Larger | 4 x 30 sec | 3, 6.6, 14.52, 6.6 (multiplicative ratio of 2.2x base Hz, close to a ninth) |
| 8 | Duty Cycle Shift Small | 4 x 30 sec | 50, 55, 60, 65 |
| 9 | Duty Cycle Shift Moderate | 4 x 30 sec | 40, 50, 60, 70 |
| 10 | Duty Cycle Shift Larger | 4 x 30 sec | 25, 50, 75, 50 |
| 11 | Dynamic sequence | 120 sec | Combination of the above parameters |

Figure 2. Individual Stroboscopic Stimulation Session Parameters for Work Package 1.

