As this study is collecting preliminary data to inform the development of a stroboscopic intervention in WP2, we will not be discontinuing the intervention unless requested to by the participant;however, in the case of the current experiment if participants report a tolerability score of 7 or above, thatarm of the study will be halted immediately. If an adverse medical reaction occurs, all testing with that participant will be halted.

C. STRATEGIES TO IMPROVE ADHERENCE TO INTERVENTION PROTOCOLS, AND ANY PROCEDURES FOR MONITORING ADHERENCE

As this is a one-time (1hr) experiment, the adherence will only be monitored within the protocol of the study. Online pre-screening and consent collection ensure informed participation. Researchers will monitor participant experiences throughout testing and offer flexibility in scheduling when needed. Participants receive 10 GBP per hour or SONA credits for engagement with this study.

Experiments are run in the laboratory with a researcher present at all times; participants will be guided and monitored through the entirety of the experiment, guaranteeing the correct administration of the study protocol. All researchers follow an agreed-upon script to reduce researcher bias across the study.

D. RELEVANT CONCOMITANT CARE AND INTERVENTIONS THAT ARE PERMITTED OR PROHIBITED DURING THE TRIAL

Participants undergoing psychotropic treatment or additional talk-based therapeutic interventions are not excluded from participation in this study, but the medication or supplement and self-reported familiarity with their psychotropic treatment will be recorded.

12. PRIMARY, SECONDARY, AND OTHER OUTCOMES, INCLUDING THE SPECIFIC MEASUREMENT VARIABLE, ANALYSIS METRIC, METHOD OF AGGREGATION, AND TIME POINT FOR EACH OUTCOME; EXPLANATION OF THE CLINICAL RELEVANCE OF CHOSEN EFFICACY AND HARM OUTCOMES IS STRONGLY RECOMMENDED

Primary outcome:

- Safety outcomes: no adverse medical incidents (no medical intervention needed)
- Maximum tolerability score per 30 second section (0-10 scale)

Data from Dreamachine suggests a high safety and tolerability profile to stroboscopic stimulation in the general population. However, we need to assess if this is also th case in MDD

The safety outcomes are crucial in assessing the risks of stroboscopic light for people with MDD. If medical intervention is required due to the administration of (certain parameters) of strobe light, their administration will not be appropriate in this population.

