| Have you ever had an adverse reaction to flickering or bright lighting? | Yes/No |
| Do you suffer from frequent or severe headaches including migraines? | Yes/No |
| Are you currently pregnant? | Yes/No |

-

33e. Tolerability Questions

Participants be shown the list of symptoms they reported to have experienced and will rate them as follows:

How much discomfort did the symptoms to have experienced caused you, select a number from the discomfort scale.

32f. Demographic Questions

| How old are you? | Number Input |
|---|--------------|
| What is your biological sex? | Female |
| | Male |
| | Other |
| What is your gender? (if you feel comfortable to share this) | Female |
| | Male |
| | Other |
| I am currently experiencing symptoms associated with depression, such as low mood or sadness, for extended periods of time. | Yes |
| | No |
| Do your symptoms of depression display a seasonal pattern? Are your symptoms usually more apparent and more severe during the winter? | Yes |
| | No |

| If you answered 'Yes' please provide more detail about your seasonal pattern of depression. | Text Input |
|---|-----------------------|
| Are you currently taking any medications, herbs, or supplements to treat your depression? | Yes |
| | No |
| If you answered 'Yes', this is not necessarily a problem for you to take part in this study. Please provide details of the treatment, including the name, dosage, and frequency of use. | Text Input |
| Have you been taking this medication long enough to consider it as familiar to you? | Yes |
| | No |
| | I don't know |
| Are you planning to change or start treatment for your depressive symptoms in the next EXPECTED TESTING DURATION, this includes therapy, medication or other interventions? | Yes (with text field) |
| | No |
| Are you currently being treated with any antipsychotic drugs (e.g. Chlorpromazine or Haloperidol)? | Yes |
| | No |
| Do you have a history of substance misuse (or substance abuse), or currently have issues relating to substance misuse (or substance abuse)? | Yes |
| | No |

| | Prefer not to say |
|--|-------------------|
| Do you have a history of, or current diagnosis of: psychosis, bipolar disorder, Parkinson's, dementia, or Alzheimer's disease? | Yes |
| | No |
| If you answered 'Yes' to the above question, which current diagnosis do you have? | Text Input |
| Do you have any history of Traumatic Brain Injury (TBI)? | Yes |
| | No |

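### Section-level tolerability scores must be rebuilt from one post-session rating per symptom plus optional recall, and the section-worded rule does not reach session 11

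*Protocol*

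**What the plan says.** Section 12 of the protocol lists the primary tolerability outcome as "Maximum tolerability score per 30 second section (0-10 scale". Section 20A takes each participant's maximum score within a section. It calls a section tolerable if the upper limit of the 80% confidence interval across participants is below 7. Participants who report no symptoms receive 0 in the relevant sections.

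Measurement follows the session, not the section:

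- The interventions section (part A, after the eligibility criteria) states "After each 2-minute session, participants will be asked whether they had any side effects", and section 12.4 gives the same time point.
- On severity, part A says "Any reported side effect will then be rated on a 10-point scale". The item in Appendix 33e reads "How much discomfort did the symptoms to have experienced caused you, select a number from the discomfort scale" and names no section.
- On location, section 12.5 says "we will ask participants to indicate (if possible) in which 30-second section of a session these side effects occurred". The same section defines a session score, the highest rating for any symptom in that block. Section 14 bases the sample size on that session score.

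On structure, part A says "The first 10 sessions are divided into four 30-second sections". Of the remaining one it says "The final session (session 11) will contain a combination of all tested parameters"; Figure 2 shows it as a single 120-second run.

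**The concern.** The unit that is judged is finer than the unit that is rated. Over sessions 1 to 10 the rule needs 40 section scores per participant, and these come from 10 rating occasions. The bridge between the two is a location question that the participant may be unable to answer. The protocol does not say what happens to the rating when that occurs, or how one rating is shared among several sections when a symptom lasts or changes.

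Section 12 uses the tolerability score to choose parameters for the WP2 intervention, so an undefined score leaves that choice open to a convention adopted after the data are seen. Separately, a rule worded by section has nothing to act on in session 11, the only session in which the tested parameters are combined.

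**Working it through.** **The plan's own figure.** Section 14 asks for 25 participants and allows 20% dropout: 25 / (1 − 0.20) = 31.25, rounded up to 32. The stated total reproduces. The base of 25 rests on a cited guideline and cannot be derived from the protocol. It was set for the session score, whereas the rule uses the section score.

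**Which section scores exist.** Setting sections 12, 12.5, 20A, part A and Appendix 33e side by side:

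| Participant's report for a session | Section score |
|---|---|
| No symptoms | Defined: 0 (section 20A) |
| Symptom placed in one section | Derivable: its rating in that section |
| Symptom placed in several sections | One rating only; severity in each section cannot be recovered |
| Symptom that cannot be placed | None defined |
| Any symptom in session 11 | No sections; only a session score |

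**Can the handling change a verdict?** Section 20A does not say what the 80% interval is for. I assume a two-sided t-interval for the mean. I also assume that everyone rates either 8 or 0, and that all who can place the symptom name the same section. If k of n analysed participants score 8:

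- mean m = 8k/n
- variance s² = 64·k(n − k) / [n(n − 1)]
- upper limit U = m + t·s/√n, with t the 90th percentile on n − 1 degrees of freedom

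Take 25 participants, 20 rating 8 and 5 of those 20 unable to place it. For the section named by the other 15:

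- Session score given to every section: k = 20, n = 25. m = 6.40, s² = 64·20·5/600 = 10.67, s/√n = 0.653, t = 1.318, U = 7.26.
- Unplaced ratings dropped: k = 15, n = 20. m = 6.00, s² = 64·15·5/380 = 12.63, s/√n = 0.795, t = 1.328, U = 7.06.
- Unplaced ratings counted as 0: k = 15, n = 25. m = 4.80, s² = 64·15·10/600 = 16, s/√n = 0.800, t = 1.318, U = 5.85.

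Upper limits for this and two other assumed patterns:

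| Pattern, 25 participants | Session score to every section | Dropped | Counted as 0 |
|---|---|---|---|
| 20 rate 8, 5 unplaced | 7.26 (fails) | 7.06 (fails) | 5.85 (passes) |
| 20 rate 8, 10 unplaced | 7.26 (fails) | 6.69 (passes) | 4.25 (passes) |
| 10 rate 8, 5 unplaced | 4.25 (passes) | 3.06 (passes) | 2.46 (passes) |

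On the same reading, with all others at 0, a section fails at n = 25 only if at least 20 participants score 8, or 17 score 9, or 15 score 10. At n = 32 the counts are 25, 22 and 19. The convention therefore matters only when discomfort is widespread.

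**Session 11.** The section rule covers 10 × 4 = 40 sections and none of session 11. That leaves 1 of 11 sessions without a verdict under section 20A.

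**The case against.** The strongest reply is that the protocol collects what it needs. Every symptom is rated, its section is asked for within minutes, and symptom-free sessions are set to 0. A rating plus a location gives a section score. How to score incomplete answers is the sort of detail left to a statistical analysis plan, which may exist but is not at hand. Most of this stands. A reader might infer that the rule runs on scores that are never collected, and the text does not support that. The gap is confined to unplaced and multi-section symptoms. For the multi-section case, however, an analysis plan could add a convention but could not recover a rating that was never requested.

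A reader might also infer that unplaced symptoms drop out and tilt the results towards tolerable. Nothing in the protocol says they are dropped; giving them to all four sections fits the text equally well. The direction of any bias depends on the missing rule and on how people rate. A single rating that reflects the worst moment would push milder sections upwards.

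A third inference would be that session 11 is never judged. It is rated like every other session, and the primary safety outcome covers it. The exclusion sentence in section 12 speaks of parameters rather than sections and might extend to it. The gap is in the operative rule, not in the data. Nor is the session score idle: the halting provisions for individual participants act on high ratings given after a session.

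**Conclusion.** The mismatch between outcome and measurement is real and lies in the protocol itself. Section scores are reconstructed from one post-session rating per symptom plus optional recall. They are undefined for symptoms that cannot be placed and not recoverable for symptoms that span sections. The rule in section 20A gives no verdict on the one combined exposure, although a score for it exists.

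The size is limited. In the assumed example the upper limit runs from 5.85 to 7.26, on either side of 7, according to the convention alone. With 10 of 25 rating 8 and 5 of them unplaced, every convention passes. These figures rest on a t-interval for the mean and on invented scores; the share of symptoms that cannot be placed is unknown. They show that the choice can matter, not that results will be wrong. The sample size of 32 is unaffected.

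**What to change.** Keep the section outcome for sessions 1 to 10 and make three changes:

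1. After any session with symptoms, ask for one overall 0–10 discomfort rating for each 30-second section. Keep the per-symptom ratings, because symptom intensity is a secondary outcome.
2. If that is not wanted, pre-state a conservative attribution rule: an unplaced rating counts in all four sections, and a multi-section rating counts in every section named.
3. State in section 20A that the same 80% limit rule also applies to the session maximum defined in section 12.5, for all sessions including session 11. This also links the rule to the variable used in section 14.

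The session maximum should supplement the section score, not replace it. On its own it would lose the step resolution that objective O2 needs: session 1 alone runs from luminance step 10 to step 70. The session result is also stricter by construction. If 20 of 25 rate 8, with 5 naming each of the four sections, every section has 5 of 25 (upper limit 2.46) while the session has 20 of 25 (upper limit 7.26). The text should therefore say how the two results are read together.

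The cost is some wording and a few extra clicks per symptomatic session. Section ratings given after the session are still recalled, and the conservative rule may overstate discomfort in the early sections.
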